10.3 Vital Signs and Weight

Weight and vital signs (including systolic blood pressure, diastolic blood pressure, pulse rate, respiratory rate, and body temperature) will be summarized for each treatment group. Descriptive statistics of each parameter at baseline will be provided along with the change from baseline at each subsequent visit. A subject-level listing will also be provided.

10.4 Physical Examination

Results of the general physical and knee examinations were noted in the source documents. Any clinically significant finding noted prior to study medication injection were recorded as medical history. If it was found after study medication injection, it was reported as an AE.

11. OTHER/EXPLORATORY ANALYSIS

11.1 Sites

Randomization was stratified by site and enrollment was capped at each site. Although this should minimize site differences and potential interactions, exploratory analyses taking site into account may be conducted if anomalies in the data are observed.

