10.6 MEASURES TO MINIMIZE BIAS

10.6.1 BLINDING PROCEDURES

This is a double-blind study. Study medication will be provided to the investigational center, which must identify unblinded personnel who are able to prepare and perform the injection of study medication. Study personnel administering or preparing study medication must minimize any contact with the subject following the injection and may not perform any study assessments throughout the duration of the study. Each site will be required to document a blinding plan that identifies the blinded and unblinded personnel at the investigational center and describes how the study blind will be maintained.

Subjects will be assigned a subject number at the Screening Visit. On Day 1, eligible subjects will be randomized via the Medidata Rave database. Upon randomization of a subject, an email with the subject's corresponding kit number will be sent from Medidata (*[contact]*) to the investigational staff member designated to dispense study medication. Subjects will be randomized 1:1 (0.07 mg active per 2 mL injection: 2 mL placebo) to each treatment group using a permuted block design. Specific information regarding the use of Medidata Rave Randomization and Trial Supply Management (RTSM) to store and implement the permuted block design will be detailed within the SAP.

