4.2 Method of Treatment Assignment and Randomization

Subjects were randomized 1:1 (0.07 mg active per 2 mL injection:2 mL placebo) to each treatment group using Medidata Rave Randomization and Trial Supply Management (RTSM) with a permuted block design stratified by study site. 250 blocks of size 6 were generated for a total of 1500 possible subject slots.

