7.1.3 Analysis of Covariance

Analysis of Covariance (ANCOVA) will be used for continuous efficacy outcome measures to test the following hypotheses:

$$H_0: (\beta_1 - \beta_0) = 0$$

$$H_A: (\beta_1 - \beta_0) \neq 0$$

In the statement above, β is the least squares estimate in the change in the continuous efficacy outcome from baseline, where β_0 is the estimate for placebo and β_1 is the estimate for the active treatment group. The models will be adjusted for baseline value of the outcome.

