9.2 Primary Efficacy Analysis

9.2.1 Main Analysis

Change over time in Pain NRS will be characterized using an MMRM model to estimate change from baseline with treatment group, week, treatment \times week interaction and baseline value as covariates. The model will include all timepoints for subjects in the FAS and will be evaluated at Week 12.

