9.3 Secondary Efficacy Analysis

9.3.1 Main Analysis

Change over time in secondary endpoints will be characterized using MMRM to estimate change from baseline with treatment group, week, treatment \times week interaction and baseline value as covariates. The model will include all timepoints for subjects in the FAS and will be evaluated for Pain NRS at Week 24 and WOMAC Function and Patient Global Assessment at Weeks 12 and 24.

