13. CHANGES TO PLANNED ANALYSIS

Change	Protocol Section	Rationale
Subgroup analysis in subjects having a baseline mJSW within 1.5 to 4 mm inclusive disease will not be conducted.	10.4.9	mJSW was not an inclusion criterion or an outcome measure for OA-10 and it was not assessed in all subjects

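### Randomisation is stratified by site but no planned MMRM or ANCOVA includes site, so if sites differ in outcome the reported standard error is slightly too wide

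*SAP*

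**What the plan says.** Protocol 10.6.1 allocates subjects 1:1 "to each treatment group using a permuted block design". It does not name site as a stratum and leaves the detail to the SAP. SAP 4.2 supplies it: allocation is "with a permuted block design stratified by study site", with 250 blocks of 6 (1,500 slots). No other stratification factor is given.

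The efficacy models do not use that factor:

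- SAP 9.2.1 (primary): "Change over time in Pain NRS will be characterized using an MMRM model to estimate change from baseline", with arm, week, their interaction and the baseline score as the only terms.
- SAP 9.3.1 (secondary): "Change over time in secondary endpoints will be characterized using MMRM to estimate change from baseline", with the same terms. Protocol 10.4.2 and 10.4.3 give the same models.
- SAP 7.1.3 (ANCOVA): "The models will be adjusted for baseline value of the outcome". In Appendix 3, Sensitivity 2 also adds change in Total NSAID Score.

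Site appears in SAP 11.1, under other and exploratory analyses. Of the site stratification and enrolment caps it says: "Although this should minimize site differences and potential interactions". It then adds that "exploratory analyses taking site into account may be conducted if anomalies in the data are observed". The single entry in SAP Section 13 concerns something else: "Subgroup analysis in subjects having a baseline mJSW within 1.5 to 4 mm inclusive".

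**The concern.** A design that balances arms within site takes most of the site-to-site variation out of the treatment difference. A model that ignores site still counts that variation as residual noise. The standard error, confidence interval and P value then describe a less precise trial than the one that was run. The error goes one way only, towards conservatism.

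The rationale in SAP 11.1 does not close the gap. Stratification balances the arms within each site. It does not make outcomes at different sites more alike, and it does not reduce any variation in treatment effect between sites. The section then leaves site adjustment to a judgement made after looking at the data, without defining an anomaly, the model or who decides.

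What is at stake is modest. Formal testing stops at the first non-significant result, and Pain NRS at Week 12 comes first, so a slightly inflated standard error matters only near the threshold. For example, if the standard error is 3.6% too wide, a result with z = 1.96 on the correctly sized error is reported as 1.96 / 1.036 = 1.89, P about 0.058.

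**Working it through.** **Inputs from the documents.** SAP 5 (re-estimated): about 500 randomised, 225 evaluable per arm, 10% dropout; Pain NRS difference 0.8, follow-up SD 2.4; WOMAC Function difference 7.5, follow-up SD 25; baseline correlation 0.25; alpha 0.05. SAP 7.1.2: two-sided. SAP 4.2: blocks of 6 within site. Protocol 4.1: about 100 centres.

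**Assumptions, not in the documents.** The site intraclass correlation (ICC, the between-site share of residual variance) is taken as 0 to 0.15. Site sizes are taken as uneven (gamma-distributed).

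**Step 1. Reproduce the stated power.**
- Pain NRS residual SD = 2.4 × √(1 − 0.25²) = 2.324. SE = 2.324 × √(2/225) = 0.219. Power = Φ(0.8/0.219 − 1.96) = 95.5%; the SAP states 94.3%.
- WOMAC Function residual SD = 25 × 0.968 = 24.2. SE = 2.28. Power = Φ(7.5/2.28 − 1.96) = 90.8%; the SAP states 89.8%.

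The SAP used 1,000 simulations. For Pain NRS the Monte Carlo SE is √(0.943 × 0.057/1000) = 0.7 points, so the agreement is adequate.

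**Step 2. Bound the effect.** If every site were perfectly balanced, the true SE would be 0.219 × √(1 − ICC). At ICC 0.10 that is 0.219 × 0.949 = 0.208, so the reported SE would be 1/0.949 = 1.054 times the true one. With about 5 subjects per site (500/100) and blocks of 6, many blocks stay incomplete, so the real effect is smaller.

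**Step 3. Allow for incomplete blocks.** Exact variances were averaged over 3,000 simulated allocations (500 subjects, 100 uneven sites, 10% random dropout). Type I error without site is 2 × [1 − Φ(1.96 × reported SE / true SE)]. Power without site is Φ((Δ − 1.96 × reported SE) / true SE).

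| ICC | Reported SE | True SE | Excess | Type I error | NRS power, no site → random site | WOMAC Function power, no site → random site |
|---|---|---|---|---|---|---|
| 0 | 0.219 | 0.219 | 0% | 0.050 | 95.4 → 95.4% | 90.6 → 90.6% |
| 0.05 | 0.219 | 0.215 | 1.8% | 0.046 | 95.7 → 96.0% | 91.0 → 91.7% |
| 0.10 | 0.219 | 0.211 | 3.6% | 0.042 | 96.0 → 96.7% | 91.5 → 92.8% |
| 0.15 | 0.219 | 0.207 | 5.6% | 0.039 | 96.3 → 97.3% | 91.9 → 93.9% |

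The random intercept reduces the true SE by only 0, 0.2, 0.5 and 1.1%. Its main effect is to make the reported SE match the true one. With 60 sites the excess at ICC 0.10 is 4.0%; with less uneven sites it stays at 3.6%.

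**Step 4. Simulate with estimated variances.** In 20,000 trials per ICC, at ICC 0.10 the ANCOVA without site gave empirical SD 0.212, mean SE 0.219 and type I error 0.042. A REML random-site model gave 0.211, 0.210 and 0.049. Across all ICCs the random-site type I error was 0.049 to 0.053 (Monte Carlo SE 0.0015). At ICC 0 both models had 95.5% power.

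Two separate simulations agree on the model without site. At 100 sites and ICC 0, 0.05 and 0.10, one gave type I error 0.051, 0.047 and 0.044 (Monte Carlo SE about 0.0024) and the other 0.052, 0.047 and 0.040.

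**Step 5. Fixed site effects.** About 100 unpooled site terms restore the nominal level but cost power: 2.0 points at ICC 0 and 0.5 at ICC 0.10 for the 0.8-point difference. A separate simulation gave 95.6 → 93.4% at ICC 0 and 96.4 → 95.5% at ICC 0.10. Under the assumed site sizes, 18 to 23% of sites contribute one arm only.

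**Limit.** All of this is a single Week 12 timepoint. The full weekly MMRM was not simulated.

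**The case against.** The strongest reply is that nothing is broken. The error is conservative, the SAP follows the protocol's model, and the sample size was set with an ANCOVA that also omits site. Power without site is at or above the stated figure throughout the range (Pain NRS 95.4 to 96.3% against 94.3%; WOMAC Function 90.6 to 91.9% against 89.8%). The size rests on an ICC that the documents do not give; at 0 there is no error, and at 0.05 one of the simulations could not distinguish the type I error from 0.05. SAP 11.1 can also be read as referring to imbalance between arms by site, in a section that governs no confirmatory test. All of that stands, and it limits how much weight the point should carry.

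Objections to the remedy stand in part:

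- Convergence of a site intercept alongside the weekly Toeplitz structure is untested.
- The multiple-imputation model in SAP 7.1.6 uses baseline and arm only, so Sensitivity 1 would impute without site and analyse with it unless this is addressed. The models in SAP 9.4 would also need a decision.
- The fallback depends on the data, but when the site variance estimates to zero the two models coincide, so nothing is selected.
- The 100 centres were planned alongside about 726 subjects. The number that enrolled after the cut to about 500 is not stated.

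None of this gives a reason to leave out the factor used in randomisation, or to let site in only through an undefined trigger.

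**Conclusion.** The concern holds. Site is the only stated stratification factor, no planned MMRM or ANCOVA includes it, and the reason given in SAP 11.1 does not justify the omission. If sites differ in outcome, the reported standard error is too wide: by 1.8% at ICC 0.05, 3.6% at 0.10 and 5.6% at 0.15, with type I error 0.046, 0.042 and 0.039. These sizes rest on the assumed ICC, about 450 evaluable subjects, about 100 uneven sites and a single-timepoint analysis; the true effect may be near zero.

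Validity, the fixed testing sequence and the stated power are not threatened. The gain is mainly inference sized to the design, plus at most 1.0 point of power (Pain NRS) or 2.0 points (WOMAC Function) at the planned differences. At a 0.5-point NRS difference, which is an assumption and not in the documents, the gain is 0 to about 5 points.

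**What to change.** Before unblinding:

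1. Add site as a random intercept to the primary and secondary MMRMs, beside the stated Toeplitz or unstructured within-subject covariance, and to the ANCOVA sensitivity models. Name the degrees-of-freedom method.
2. State the fallback: use the model without site if the site variance estimates to zero or the model does not converge. In simulation the estimate was zero in 54% of trials at ICC 0, 7% at 0.05 and under 1% at 0.10 or more, so the rule will be needed.
3. Report the model without site as a sensitivity analysis.
4. Do not fit about 100 unpooled fixed site effects.
5. Say whether the imputation model in SAP 7.1.6 and the models in SAP 9.4 also carry site.
6. In SAP 11.1, delete the anomalies condition and correct the rationale: stratification balances arms within site and does not reduce differences between sites.
7. List the change in SAP Section 13, because protocol 10.4.2 and 10.4.3 give the model without site.

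The cost is one extra variance parameter, a RANDOM statement, a paragraph and a line in Section 13, plus a convergence check of the weekly model on blinded or simulated data. The drawback is a declared departure from the protocol's model.

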12. MEDICATIONS

The summary of medications will be performed on the SAS.

12.1 Concomitant Medication

The World Health Organization Drug Dictionary (WHODD) will be used to classify prior and concomitant medications by Anatomical Main Group (Anatomical Therapeutic Chemical, ATC, Level 1), Therapeutic Subgroup (ATC Level 2), and preferred term. Prior and concomitant medication usage will be summarized by the number and percentage of subjects receiving each medication by treatment group.

The subgroup of medications initiated after first exposure to study product will be summarized in the same manner. If a medication start or end date is incomplete, it will be imputed in a way that assumes maximum exposure time (see table below).

Partial Date Availability	Impute Start Date		Impute End Date	
Year (YYYY)	Prior to Injection year	YYYY-12-31	Prior to end of study year	YYYY-12-31
	Same as Injection year	Injection Date	Same as end of study year	End of Study Date
	After Injection year	YYYY-01-01	After end of study year	YYYY-01-01
Year and Month (YYYY-MM)	Prior to Injection year and month	YYYY-MM-[DD, last day of month]	Prior to end of study year and month	YYYY-MM-[DD, last day of month]
	Same as Injection year and month	Injection Date	Same as end of study year and month	End of Study Date
	After Injection year and month	YYYY-MM-01	After end of study year and month	YYYY-MM-01
Ongoing or unknown status at end of study (e.g., no end date and unknown whether ongoing)	Not Applicable		End of Study Date	
Additional Considerations	If the end date is not missing, and the imputed start date is after the end date, the start date will be set equal to the end date.		If the imputed end date is before the start date, then the imputed end date will be set equal to the start date.	

Subject-level listings containing prior and concomitant medications (WHODD coding), and procedures/non-drug therapies (MedDRA coding) will be provided and will display the dates as they were entered (not the imputed version described above).

12.2 Exposure and Compliance

All treated subjects received a single injection. A list of lot numbers used in this study will be provided in the clinical study report.

12.3 NSAID/Acetaminophen Usage

An NSAID/acetaminophen usage score (NSAID Score) will be computed as outlined in (Dougados, et al., 2011), adapted to this study design. General calculation for each applicable medication is as follows:

$$\text{NSAID Score} = \frac{[\text{eqNSAID}] \times [\text{Duration of Use}] \times [\text{Usual usage}]}{[\text{Time period in days}]}$$

- **eqNSAID (equivalent NSAID/Acetaminophen value):**

$$100 \times \frac{[\text{Usual total daily dose}]}{[\text{Consensus dose equivalent to 150 mg Diclofenac}]}$$

The following consensus dose equivalent settings will be used:

Reference	Medication ^c	Consensus dose equivalent to 150 mg of diclofenac (in mg)
Dougados et al Table 2 ^a	Diclofenac	150
	Diclofenac sodium	
	Cyanocobalamin;diclofenac sodium;pyridoxine hydrochloride;thiamine mononitrate	
	Naproxen	1000
	Naproxen sodium	
	Diphenhydramine hydrochloride; naproxen sodium	
	Esomeprazole magnesium; naproxen	
	Aceclofenac	200
	Celecoxib	400
	Etodolac	600
	Etoricoxib	90
	Flurbiprofen	200
	Ibuprofen	2400
	Diphenhydramine hydrochloride; ibuprofen	
	ibuprofen ;pseudoephedrine hydrochloride	
	Indometacin	150
	Ketoprofen	200
	Meloxicam	15
Additional Medications ^b	Nimesulide	200
	Phenylbutazone	400
	Piroxicam	20
	Tenoxicam	20
	Acetaminophen	3000
	Paracetamol	
	Butalbital;caffeine; paracetamol	
	Caffeine; paracetamol	
	Chlorphenamine maleate;dextromethorphan hydrobromide; paracetamol	
	Chlorphenamine maleate; paracetamol	
	Chlorphenamine maleate; paracetamol ;pseudoephedrine hydrochloride	
	Codeine phosphate; paracetamol	
	Dextromethorphan hydrobromide;doxylamine succinate;ephedrine sulfate;ethanol; paracetamol	
	Dextromethorphan hydrobromide;doxylamine succinate; paracetamol	
	Dextromethorphan hydrobromide;guaifenesin; paracetamol ;pseudoephedrine hydrochloride	
	Dextromethorphan;phenylephrine	
	Diphenhydramine hydrochloride; paracetamol	
	Diphenhydramine hydrochloride; paracetamol ;phenylephrine hydrochloride	
	Guaifenesin; paracetamol ;phenylephrine hydrochloride	
	Hydrocodone bitartrate; paracetamol	
	Hydrocodone; paracetamol	
	Oxycodone hydrochloride; paracetamol	
	Acetylsalicylic acid ;caffeine; paracetamol	3000
	Acetylsalicylic acid	3000
	Acetylsalicylic acid ;caffeine	
	Ketorolac	40
	Nabumetone	2000
	Sulindac	400

^a This full list is taken directly from (Dougados, et al., 2011) and some medications may not have been used by any subject in this study.

^b For medications not covered in (Dougados, et al., 2011), the above settings will be used based on decision by the Biosplice Therapeutics, Inc., medical director and some medications may not have been used by any subject in this study.

^c Combination medications (active ingredients are semicolon separated) are analyzed after considering the amount of the active ingredient of interest (in bold)

- **Duration of Use:** This will be equal to the number of days medication was used during each 4-week period of interest: [medication end date - medication start date] + 1 (date imputations, if applicable, are performed as described in section 12.1). If medication is ongoing or end date exceeds the period of interest, the end date will be set to the maximum date of interest. If medication start date is prior to the period of interest, the start date will be set to the minimum date of interest (i.e., the maximum possible duration of use within any given time period of interest is 28 days).
- **Usual usage:**

eCRF Option	Value used in calculation
No NSAID / Acetaminophen usage	0
>0-1 days a week	0.5 / 7
2-3 days a week	2.5 / 7
4-5 days a week	4.5 / 7
6-7 days a week	6.5 / 7

- **Time period in days:** 28 days (or 4-week periods).

The sum of all medications used for each 4-week period (Total NSAID Score) will be calculated and summarized. The time periods of interest are as follows:

Nominal Time Period	Actual Study Days
Baseline	Day -28 to -1
Day 1 to Week 4	Day 1 to 28
Week 5 to Week 8	Day 29 to 56
Week 9 to Week 12	Day 57 to 84
Week 13 to Week 16	Day 85 to 112
Week 17 to Week 20	Day 113 to 140
Week 21 to Week 24	Day 141 to 168
Week 25 to Week 28	Day 169 to 196

NSAID scores are only calculated for oral medications. If a subject did not have any NSAID/acetaminophen usage during a time period, their Total NSAID score will be set to 0 for that time period. If a subject terminated from the study early, the Total NSAID score for the period in which they terminated will be considered missing (i.e., an early termination subject must be in-study for the entire 28-day period of interest to compute an NSAID score).

A statistical description (number of subjects, mean, standard deviation, median, minimum, and maximum) of Total NSAID Score at baseline will be provided along with the change from baseline at each subsequent visit. Components of the Total NSAID Score will be provided in a

listing. Investigator assessment of NSAID/acetaminophen usage will also be provided in a listing.

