Subjects will complete the Patient Global Assessment on the Sponsor-provided electronic device. Subjects will receive notifications reminding them to complete the Patient Global Assessment.

Assessment of NSAID/Acetaminophen Usage

Information about NSAID and acetaminophen usage will be collected as part of concomitant medications at all visits. Subjects will be asked to recall the name, usual total daily dose, and usual number of days taken per week of any oral NSAID or acetaminophen medications during the previous 4 weeks. Subjects will be trained on what medications are NSAIDs at the Screening Visit. Assessment of NSAID/acetaminophen usage on Day 1 prior to study medication administration will be used to establish the subject’s baseline 4-week NSAID/acetaminophen usage and will be documented on the “NSAID/Acetaminophen usage – Day 1” eCRF.

Starting at Week 4 and at all subsequent in-person and phone visits until Week 28 (EOS)/ET, subjects will be asked about their NSAID/acetaminophen usage during the previous 4 weeks. This information (name, usual total daily dose, usual number of days taken per week) will be documented as concomitant medications. The Investigator will then compare the data with the

baseline information obtained on Day 1. If there is a change from baseline, the Investigator will first assess whether the change was clinically relevant and, if clinically relevant, whether it was due to the subject's target knee OA pain. Assessments will be documented on the "NSAID/Acetaminophen Usage (Clinical Visits or Telephone Visits)" eCRF.

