7.8 RESCUE MEDICATIONS, TREATMENTS, AND PROCEDURES

Subjects are allowed to remain on their stable regimen of NSAIDs/acetaminophen during this study and may change their usage as needed for pain management, including for the rescue of knee pain.

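### SAP 12.3 under-scores dated NSAID/acetaminophen courses shorter than a week, because a days-per-week fraction is applied to a span of less than seven days

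*SAP*

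**What the plan says.** SAP 12.3 scores each oral medication as eqNSAID × Duration of Use × Usual usage, divided by a 28-day period, and sums over medications.

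- **Duration of Use** is defined as follows: "This will be equal to the number of days medication was used during each 4-week period of interest: [medication end date - medication start date] + 1". The words describe days of use, but the formula gives a calendar span. For open records, "If medication is ongoing or end date exceeds the period of interest, the end date will be set to the maximum date of interest". The span within a period cannot exceed 28 days.
- **Usual usage:** an eCRF band converted to a weekly fraction. The lowest non-zero row reads ">0-1 days a week 0.5 / 7"; the others are 2.5/7, 4.5/7 and 6.5/7.
- **Data collected:** Protocol 7.1.1 has subjects recall the "usual number of days taken per week of any oral NSAID or acetaminophen medications during the previous 4 weeks". Protocol 7.8 lets subjects stay on a stable regimen, and they "may change their usage as needed for pain management, including for the rescue of knee pain".
- **Use of the score:** SAP 12.3 summarises Total NSAID Score descriptively and puts its components and the investigator assessments in listings. SAP Appendix 3 uses its change from baseline as a covariate in Sensitivity 2. The primary estimand (SAP 9.1) applies regardless of NSAID or acetaminophen use.

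**The concern.** Multiplying a calendar span by a weekly fraction converts the span into days of use. The conversion works when the span covers whole weeks. When a record starts and ends inside a week, its dates already bound the days of use closely, and the fraction cuts them again. The fraction never reaches 1, so a record that starts and ends on the same day is credited with between 0.07 and 0.93 of a day, although it can only contain one.

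Total NSAID Score is the only summarised measure of secondary endpoint 4, and SAP 4.4.2 relies on quantified rescue use to judge its effect on the key endpoints. If some rescue was recorded as short dated courses, the score misses part of it, and the Sensitivity 2 covariate carries the same error.

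**Working it through.** **Inputs (SAP 12.3).** Period T = 28 days. Weekly fraction u = 0.5/7 = 0.071, 2.5/7 = 0.357, 4.5/7 = 0.643 or 6.5/7 = 0.929. I set eqNSAID to 100 (the full equivalent dose); it cancels from every percentage. D is the span in days.

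**1. The plan's own figure.** The only derived figure in the section is the 28-day maximum. Day 1 to 28 gives 28 − 1 + 1 = 28; Day −28 to −1 gives −1 − (−28) + 1 = 28. It reproduces.

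**2. Where the product is right.** A record open for the whole period scores 100 × 28 × u / 28 = 7.14, 35.71, 64.29 or 92.86, the exact midpoint of each band. A 14-day span with 5 days of use, coded 2-3 days a week, scores 100 × 14 × 0.357 / 28 = 17.86, equal to 100 × 5/28.

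**3. Where it is too low.** For a course taken on every day between its dates, the plan gives 100 × D × u / 28 and the days used give 100 × D / 28, so the loss is 1 − u. If sites code the days taken in that week:

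| Course | Band | Plan's score | Days used / 28 | Loss |
|---|---|---|---|---|
| 1 day | >0-1 | 0.26 | 3.57 | 92.9% |
| 3 days | 2-3 | 3.83 | 10.71 | 64.3% |
| 5 days | 4-5 | 11.48 | 17.86 | 35.7% |
| 6 days | 6-7 | 19.90 | 21.43 | 7.1% |

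**4. Dependence on coding.**
- If sites average over the four recalled weeks, 3 days is 0.75 a week and 5 days is 1.25 a week. Both fall in or nearest the lowest band, and score 0.77 against 10.71 and 1.28 against 17.86 (93% low).
- If sites code the frequency while on the drug, every daily course is in the 6-7 band and the loss is 7.1%.

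**5. The midpoint's share.** For the one-day record, 3.57/0.26 is a factor of 14: 7 from the weekly fraction and 2 from coding the lowest band at 0.5. With 1/7 in place of 0.5/7 the score would be 0.51 and the loss 1 − 1/7 = 85.7%. The midpoint also acts alone: an ongoing user at exactly one day a week scores 7.14 against 100 × 4/28 = 14.29.

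**6. Same intake, different dating.** Take two days of use in the period. Under four-week averaging (0.5 a week, lowest band), a dated 2-day record scores 0.51 and an ongoing record 7.14. Under in-week coding the dated record falls in the 2-3 band and scores 2.55, against 100 × 2/28 = 7.14 for the days used.

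**The case against.** The strongest defence is that Duration of Use is computed as a span, whatever its description says, and that span × weekly frequency is the correct product for ongoing and as-needed use. Step 2 confirms this, and it stands. A reader might infer that the formula discounts use twice in general; it does not.

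A reader might also infer that rescue is lost after injection while the stable baseline regimen is scored correctly, so that change from baseline leans toward no increase and any between-arm difference shrinks. The documents do not establish this. Recall of a usual dose and frequency over four weeks fits one line per drug, Protocol 7.8 allows a change within an existing regimen, and the partial-date rules in SAP 12.1 can lengthen post-injection records. Nothing shows how rescue was actually dated.

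Finally, the size depends on site coding, which the documents do not settle. That also stands, so 36% to 93% cannot be given as an unconditional range. It does not rescue the rule: under every band, a one-day record receives less than one day.

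**Conclusion.** The point holds for dated records shorter than 7 days: the stated rule gives too low a score. The loss for a daily course is 7% to 93%, according to the band entered, and the 64% and 36% examples assume that sites coded the days taken in that week. The number of affected records and the direction of any between-arm effect are unknown.

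The consequence is measurement error in the descriptive summary of secondary endpoint 4 and in the Sensitivity 2 covariate. NSAID usage is not among the six hypotheses in the fixed sequence (SAP 9), and neither the primary analysis nor the main secondary MMRM analyses use the score. This should be corrected, but it does not threaten the trial's main conclusion.

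**What to change.** In SAP 12.3:

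- For records whose full length, before clipping to the 28-day period, is under 7 days, replace Duration × Usual usage with days used = the smaller of the span and the band's upper end (1, 3, 5 or 7), but not less than the smaller of the span and 2. The floor holds because the start and end dates are both days of use; it presumes entered rather than imputed dates.
- Keep span × frequency for records of 7 days or more.
- State that the frequency applies between the record's start and end dates, and define Duration of Use as the calendar span of the record rather than a count of days used.
- Recompute Total NSAID Score for endpoint 4 and Sensitivity 2. If the data are already unblinded, report it alongside the score under the present rule.

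The rule returns 1, 3 and 5 days for the 1-, 3- and 5-day examples under in-week coding (3.57, 10.71, 17.86).

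Simply setting Usual usage to 1 below 7 days would be worse. In the lowest band a 6-day record would score 100 × 6/28 = 21.43 and a 7-day record 100 × 7 × 0.071 / 28 = 1.79. A 6-day line with one day of use would be six times too high (21.43 against 3.57). Under the proposed rule that 6-day record counts 2 days (7.14), so a smaller step remains at 7 days.

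The cost is a few sentences and a programming change on data already collected. The band's upper end may overstate a short record by about a day. If sites averaged over four weeks, the repair is partial: a 5-day daily course in the lowest band rises from 1.28 to 7.14 against 17.86, and a 10-day daily course coded 2-3 stays at 12.76 against 35.71. The eCRF Completion Guidelines (Protocol 14.1) should therefore be checked for the coding instruction.
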